4 ANALYSIS AND REPORTING

4.1 Interim Analysis

No interim analysis is planned for this study.

4.2 Final Analysis

All final, planned analysis identified in the protocol and in this SAP will be performed after the study database has been locked and treatment code has been unblinded.

Any post-hoc, exploratory analysis completed to support planned study analysis, which were not identified in this SAP, will be documented and reported in appendices to the CSR. Any results from these unplanned analyses (post-hoc) will also be clearly identified in the text of the CSR.

5 ANALYSIS POPULATIONS

The following analysis populations are planned for this study:

- Safety Population (SAFETY): The Safety Population includes all subjects who are randomized into the study and receive any amount of Investigational Product (IP).
- **Intent-To-Treat Population (ITT):** The ITT Population includes all subjects who are randomized into the study.
- **Per-Protocol Population (PP):** The PP Population includes all randomized subjects who do not have any significant protocol deviations defined as a major protocol deviation. Major protocol deviations are listed in section 7 (below). Membership in the PP population will be determined by a blinded review of patient data prior to database lock.

5.1 Sample Size

Enrollment of 90 subjects is expected to yield 80 subjects who complete the study as planned. Assuming an effect size of 0.7, this number will provide approximately 90% power to detect a significant difference between the treatments based on a 2-tailed $\alpha = 0.05$ comparison of mean change from baseline.

6 GENERAL ISSUES FOR STATISTICAL ANALYSIS

6.1 General Statistical Methodology

Data processing, tabulation of descriptive statistics, calculation of inferential statistics, and graphical representations will be performed using SAS® Software (release 9.3 or higher) for Windows, unless otherwise specified.

Continuous (quantitative) variables will be summarized using descriptive statistics including number of non-missing values, mean, standard deviation (SD), median, minimum, and maximum. Where appropriate, estimates will be presented with 95% confidence intervals (CIs).

Categorical (qualitative) variables will be summarized using the number and proportion of each possible value. In general, the denominator for the percentage calculation will be based upon the total number of subjects in the study population for the treatment group. 95% CIs of proportions may also be presented for selected endpoints where applicable. Zero-count levels of variables will not display a percentage.

The minimum and maximum will be reported with the same degree of precision (i.e., the same number of decimal places) as the raw data. Measures of location (mean and median) will be

SAP FINAL Version 2.0

reported to 1 degree of precision more than the raw data and measures of spread (standard deviation) will be reported to 2 degrees of precision more than the raw data.

All statistical tests will be conducted at the 0.05 significance level using 2-tailed tests, and P-values will be reported. Assessments done on unscheduled visits will not be summarized but will be listed.

Page 12 of 88

In general, baseline and safety tables will be completed for the Safety Population unless otherwise specified. Efficacy tables for primary and secondary endpoints will be presented for the ITT Population. However, analyses of the PP Population may be performed if warranted by the data. These potential PP tables are not present in the table index.

All final, planned analyses identified in the protocol and in this SAP will be performed after all relevant study data have been processed and integrated into the analysis database, analysis populations have been finalized, and the database has been locked. Any post-hoc, exploratory analysis completed to support planned study analyses, which were not identified in this SAP, will be documented and reported in Section 9.8 of the Clinical Study Report (CSR). Any results from these unplanned analyses (post-hoc) will also be clearly identified as such in the text of the CSR.

6.2 Data Adjustments, Handling, Conventions

All collected data will be presented in listings. Data not subject to analyses according to this plan will not appear in any tables or graphs but will be included only in the data listings.

Adverse events will be coded using the MedDRA (version 19.0). Concomitant and Prior medications will be coded using WHO-DD (version March 1, 2016).

If partial dates occur, the convention for replacing missing dates for the purpose of calculating derived variables is as follows:

For partial start dates:

- If the year is unknown, then do not impute the date but assign a missing value.
- If the month is unknown, then:
 - o If the year matches the year of the randomization date, then impute the month and day of the randomization date.
 - o Otherwise, assign 01 January
- If the day is unknown, then:
 - o If the month and year match the month and year of the randomization date, then impute the day of the first dose date.
 - o Otherwise, assign 01.

For partial end dates:

- If the year is unknown, then do not impute the date but assign a missing value.
- If the month is unknown, then assign the last day of the year 31 December.
- If the day is unknown, then assign the last day of the month.

If an AE has a missing severity, it will be imputed as 'Severe'; any missing relationship to study drug of an AE will be imputed as 'Related'.

SAP FINAL Version 2.0

For the primary endpoint, ADHD-RS-5, missing observations will be imputed by the LOCF method (as described in section 8, below). Other ADHD-RS-5 subscales will impute the value of a missing result if enough data is present (as described in section 6.3).

Page 13 of 88

No other missing data will be imputed.

In general, for quantitative laboratory values reported as '<' or '\(\sigma'\), the lower limit of quantitation (LLOQ) or limit of detection (LOD), one-half of the reported value (i.e., LLOQ, LOD) will be used for analysis.

For quantitative laboratory values reported as '>' or '≥', the upper limit of quantitation (ULOQ), the reported value (i.e., ULOQ) will be used for analysis.

For analysis purposes, repeat laboratory test results will not be used unless the original laboratory value is missing or indicated as invalid, in which case the first non-missing repeat laboratory value will be used for data analysis.

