# 11.2 Management of Adverse Events

Adverse events will be collected from the time of signing informed consent form (ICF) through the Follow-up Visit or Early Termination Visit, whichever occurs first.

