- SCARED Significant School Avoidance is the summation of questions 2, 11, 17, and 36.
- SCARED Total Score is the summation of all 41 questions, each scored from 0 to 2 scale.
- C-SSRS Suicidal Ideation is an indicator of any subject who experience any one of the five suicidal ideation events at least once (Questions 4, 6, 8, 10, and 12)
- C-SSRS Suicidal Behavior is an indicator of any subject who experience any one of the suicidal behavior events at least once (Questions 22, 26, 29, 32, and 35)
- C-SSRS composite endpoint of Suicidal Ideation or Behavior is an indicator of any subject who experiences any one of the ten suicidal ideation or behavior events at least once.
- TEAE An AE is defined as treatment emergent if the first onset or worsening is after the first administration of IP (NFC-1 or placebo) and not more than 7 days after the last administration of IP
- For the tabulation of TEAE's that are related to study drug, these are defined as any TEAE which is determined by the investigator as 'possibly related' or 'related'.
- Post-Treatment AE is an AE that has started more than 7 days after last administration of IP.
- Prior medications are defined as medications or therapies initiated prior to date of first dose of IP and terminating prior to date of first dose of IP. Medications that are started prior to the date of first dose of IP and are continuing after the first dose of IP are considered to be both prior and concomitant medications
- Concomitant medication is defined as any medication a subject received concurrently with study treatment.
- Post-treatment medication is defined as any medication that has started more than 7 days after the last administration of IP.
- Compliance (Overall) = $(\sum (Individual Week Compliance) * (Time-Weight)) * 100. A subject is non-compliant if they take <math>< 80\%$ or > 120% of IP.
 - Individual Week Compliance is defined as the number of capsules taken at a particular week divided by the expected number of capsules taken at a particular week. Given that a subject will be dose optimized, the number of expected capsules will vary according to which dose the subject is currently on for each day.
 - Time-Weight is the fraction of \mathbf{x}/\mathbf{y} where \mathbf{x} is the number of days in the week the subject is expected to be on dose and \mathbf{y} is the whole treatment duration defined as first dose last dose + 1.

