9.1 Adverse Events

The causal relationship of the AE to the study drug is determined by the investigator as 'not related', 'unlikely/remotely related', 'possibly related', or 'related'. Any AE determined as

SAP FINAL Version 2.0

'possibly related' or 'related' will be considered 'potentially related' to study drug for purposes of analysis of these events.

Page 18 of 88

Missing and partially missing AE start and/or stop dates will be imputed for the purpose of statistical analysis, according to the specifications described in Section 6.2.

Summaries of incidence rates (frequencies and percentages) of individual TEAEs by MedDRA SOC and preferred term will be prepared. Such summaries will be displayed for TEAEs, SAEs, TEAEs leading to early termination, TEAEs by relationship to study drug, TEAEs by severity, TEAEs occurring in more than 5% of subjects, and Post-treatment AEs.

Each patient/subject will be counted only once within each preferred term If a subject experiences more than one TEAE within a preferred term only the TEAE with the strongest relationship or the maximum intensity, as appropriate, will be included in the summaries of relationship and intensity.

Subject listings of all AEs and SAEs, will be presented.

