<soc 2=""></soc>	xx (xx x%)	xx (xx x%)	xx (xx x%)	xx (xx x%)	xx (xx x%)
<event 1=""></event>	xx (xx x%)	xx (xx x%)	xx (xx x%)	xx (xx x%)	xx (xx x%)
<event 2=""></event>	xx (xx x%)	xx (xx x%)	xx (xx x%)	xx(xxx%)	xx (xx x%)
<event 3=""></event>	xx (xx x%)	xx (xx x%)	xx (xx x%)	xx (xx x%)	xx (xx x%)
<soc 3=""></soc>	xx (xx x%)	xx (xx x%)	xx (xx x%)	xx (xx x%)	xx (xx x%)
<event 1=""></event>	xx (xx x%)	xx (xx x%)	xx (xx x%)	xx (xx x%)	xx (xx x%)
<event 2=""></event>	xx (xx x%)	xx(xxx%)	xx (xx x%)	xx (xx x%)	xx (xx x%)
<event 3=""></event>	xx (xx x%)	xx (xx x%)	xx (xx x%)	xx (xx x%)	xx (xx x%)

Note: Percentages are 100*n/N. Subjects were counted only once for each System Organ Class (SOC) or Preferred Term. TEAE is defined as AEs occurring or worsening with an onset at the time of or following the start of treatment with study medication. TEAE = Treatment-Emergent Adverse Event.

[1] Adverse Events were coded from MedDRA (version xx x).

Source: Listing 16.2.6.1

Table 14.3.1.3

Incidence of TEAEs occurring in more than 5% of subjects by Randomized Treatment

{Similar shell as Table 14.3.1.2; Source: Listing 16.2.6.1} {Update footnote to add definition of TEAE, update first row of table}

Safety Population

Table 14.3.1.4
Incidence of Post-Treatment AEs by Randomized Treatment
Safety Population

{Similar shell as Table 14.3.1.2; Source: Listing 16.2.6.1} {Update footnote to add definition of TEAE, update first row of table}

Table 14.3.1.5
Incidence of SAEs by Randomized Treatment
Safety Population

{Similar shell as Table 14.3.1.2; Source: Listing 16.2.6.2} {Update footnote to add definition of SAE, update first row of table}

Table 14.3.1.6
Incidence of TEAEs Leading to Early Termination by Randomized Treatment Safety Population

{Similar shell as Table 14.3.1.2; Source: Listing 16.2.6.3} {Update update first row of table}

Table 14.3.1.7 Incidence of Deaths by Randomized Treatment Safety Population

{Similar shell as Table 14.3.1.2; Source: Listing 16.2.6.1} {Update update first row of table}

Page 1 of x Final

Table 14.3.1.8
Incidence of TEAEs by Relationship to Study Drug by Randomized Treatment
Safety Population

Preferred Term [1]	NFC-1	Placebo
Causality	(N=xx)	(N=xx)
Number of Subjects with at least one TEAE	xx (xx.x%)	xx (xx.x%)
Potentially Related	xx (xx x%)	xx (xx.x%)
Not Related	xx (xx x%)	xx (xx.x%)
<soc 1=""></soc>	xx (xx x%)	xx (xx.x%)
Potentially Related	xx (xx x%)	xx (xx.x%)
Not Related	xx (xx x%)	xx(xx.x%)

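### The SAP 6.2 unknown-day rule can date an event that ended before dosing to the first-dose date, later than its own recorded stop

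*SAP*

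**What the plan says.** SAP 6.2 handles a partial start date with an unknown day as follows: "If the month and year match the month and year of the randomization date, then impute the day of the first dose date". In any other month the day becomes 01. The end-date rules are separate and make no reference to the start: "If the day is unknown, then assign the last day of the month", while a complete stop date is left as recorded.

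SAP 9.1 applies these conventions to adverse events without adding a check: "Missing and partially missing AE start and/or stop dates will be imputed for the purpose of statistical analysis".

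Two definitions of a treatment-emergent event are in force. SAP 6.3, like Protocol 11.1.5, says "An AE is defined as treatment emergent if the first onset or worsening is after the first administration of IP", with an upper limit of 7 days after the last dose. The footnote to the Table 14.3.1.2 shell in SAP Appendix A says "TEAE is defined as AEs occurring or worsening with an onset at the time of or following the start of treatment with study medication".

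For medications, SAP 6.3 says "Prior medications are defined as medications or therapies initiated prior to date of first dose of IP and terminating prior" to that same date. Concomitant medications are those taken concurrently with study treatment.

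Protocol 11.2 collects adverse events from the signing of consent, and Protocol 11.2.3 records a stop date. Screening is at about Day -21, randomization on Day -1 and first dose on Day 1 (Protocol 7.1 and 10.1).

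**The concern.** Moving an unknown onset to the first-dose date is a usual cautious choice when the event might have begun on treatment. When the recorded stop is earlier than the first dose, that possibility is gone. The rule as written still moves the start, which creates a record that begins after it ends.

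An event that the data place wholly before treatment may then enter the TEAE tables. In the NFC-1 arm it would fall under 100 mg in the tables by dose at onset, since every subject starts at that level. If its relationship is also missing, SAP 6.2 imputes it as related.

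For medications, the moved start means the drug was no longer initiated before first dose, and its stop shows that it was not taken concurrently. It then fits neither summary table.

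**Working it through.** The plan states no figure on this point, so there is none to reproduce. The check applies the rule literally.

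**One record (assumed dates).** Randomized 20 March, first dose 21 March. An AE has its start recorded as March with the day unknown, and its stop as 10 March.
- The start month equals the randomization month, so the imputed start is 21 March.
- 21 March is 11 days after the recorded stop of 10 March.
- The imputed start equals the first-dose date and is never later than it. Onset at the start of treatment counts under the Table 14.3.1.2 footnote. Under SAP 6.3, which requires onset after first administration, a same-day start with no time is a tie.
- A drug with the same dates has an imputed start of 21 March, so it is not prior. It stopped on 10 March, so it is not concomitant.

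**When the error does not arise.**
- The stop day is also unknown: the stop becomes month-end, so no inversion results.
- The start month is earlier than the randomization month: the start becomes day 01, which is before dosing.
- Randomization is on the last day of a month and first dose on the 1st of the next: the rule read literally gives day 01 of the randomization month, again before dosing.

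**What share of qualifying records is affected?** A qualifying record has an unknown start day and a known stop before first dose. The documents give no distribution of onsets or durations, so assume every onset/stop pair in the 21 days before first dose is equally likely.

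*Closed form, 30-day month.* An onset u days before first dose (u = 1 to 21) has u possible pre-dose stop days. It falls in the same month with probability about 1 - u/30.
- Sum of u = 231; sum of u² = 3,311.
- Share = 1 - (3,311/231)/30 = 1 - 14.33/30 = 0.522.

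*Full enumeration, 365-day year, first dose the day after randomization.*
- Total records: 365 × 231 = 84,315.
- With randomization on day d of a month (not its last day), d(d+1)/2 pairs begin in that month for d up to 21, and 231 pairs thereafter. The last day contributes none.
- The sum over d = 1 to 21 is 21 × 22 × 23/6 = 1,771.
- 31-day month: 1,771 + 9 × 231 = 3,850. 30-day month: 1,771 + 8 × 231 = 3,619. 28-day month: 1,771 + 6 × 231 = 3,157.
- Year: 7 × 3,850 + 4 × 3,619 + 3,157 = 44,583.
- Share = 44,583/84,315 = 52.9%.

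The same 52.9% have both a start after their stop and a start on the first-dose date. Capping the imputed start at a known earlier stop takes both to 0%.

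**Effect of one record.** With about 45 subjects per arm (Protocol 7.1), one extra subject is 1/45 = 2.2 percentage points. This is a maximum: SAP 9.1 counts each subject once per preferred term, so a subject with a genuine TEAE of the same term adds nothing.

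**The case against.** The strongest reply is that the rule rarely bites and does little when it does. It needs a known start month, an unknown start day, a known stop before dosing, and the randomization month. Events are asked about at Screening, at the wash-out call and at Baseline. Start and stop dates and times are collected, and data management runs consistency checks and queries. Safety summaries are descriptive, no analysis of event duration is planned, and the rule is the same in both arms. Imputation serves derived variables, so the listings still carry the event or drug. All of this stands and limits the point to a minor one. It does not remove it: the raw record (month-only start, earlier full stop date) is not inconsistent, so an edit check on raw dates would not flag it. The inversion appears only when the start is imputed.

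A reader might go further than the documents allow in three ways.
- *That the event is certainly counted as treatment-emergent.* It is under the table footnote. Under SAP 6.3 and Protocol 11.1.5 it is a tie, and the SAP does not say which wording is to be programmed.
- *That about 63% of qualifying records are affected.* Averaging 1 - u/30 over u = 1 to 21 gives 1 - 11/30 = 0.633, but that ignores the requirement that the event stopped before dosing. It would hold only if events were so short that onset day made no difference to meeting that requirement.
- *That washed-out ADHD drugs vanish from the prior-medication table.* Those already in use at screening will mostly have started in earlier months; they take day 01 and stay prior. Only drugs started and stopped within the pre-dose part of the randomization month, with the start day unknown, are exposed.

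**Conclusion.** The point holds in limited form. It concerns a stated rule that gives a wrong result in an identifiable case: a start imputed after a known stop. The inversion does not depend on which TEAE definition is used. TEAE status does, and the two wordings conflict.

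About half of qualifying records (52-53%) would be affected, on the assumption that all onset/stop pairs in the 21 days before dosing are equally likely. That figure is illustrative and is not a forecast. The number of qualifying records cannot be known from the documents and is probably small. Each adds at most 2.2 points to a preferred-term incidence. The consequences are confined to TEAE counts and the prior/concomitant medication tables; the listings and the primary efficacy analysis are unaffected. It is worth correcting because the correction is so cheap.

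**What to change.** Replace the unknown-day line in SAP 6.2 with three conditions:
- If the month and year match those of first dose and the stop date is missing or on/after first dose, impute the first-dose date.
- If the stop date is before first dose, impute a pre-dose start: for AEs, the later of the first of the month and the consent date; for medications, the first of the month.
- No imputed start may be later than a known stop date. Apply this to the unknown-month line too, which has no stop-date check either.

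Matching on the first-dose month also stops the line from mixing the randomization and first-dose dates.

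Align the TEAE wording in SAP 6.3 with the Table 14.3.1.2 footnote, stating explicitly whether an onset on the first-dose date counts. This is still needed after the date rule is corrected, because every start that is properly set to the first-dose date meets the same tie.

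The cost is a short edit to SAP 6.2, one condition in the date-imputation code, and one harmonized definition. No data collection changes.

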6.3 Derived and Computed Variables

- Baseline = the last non-missing measurement/assessment before the date of first dose will be flagged. Typically, this will be the value recorded on Day -1.
- Study Day = Assessment Date Date of Randomization + 1
- Change from Baseline = Value at Post-Baseline Value at Baseline
- % Change from Baseline = 100 * Change from Baseline / Value at Baseline
- "Screen Failure" is a patient who has not met eligibility criteria, or otherwise chose not to participate in the study prior to randomization
- ADHD-RS-5 subscales if at least 80% of the questions needed to calculate a scale or subscale score have valid responses, then that score will be computed as the sum of all non-missing items divided by the percentage of items in that scale or subscale present. If fewer than 80% of items have valid responses, then that score will be assigned as missing.
- ADHD-RS-5 Inattention subscale is computed by summing the first 9 item scores for Question 4 Question 12.
- ADHD-RS-5 Hyperactivity-Impulsivity subscale is computed by summing the second 9 item scores for Question 19 Question 27.
- ADHD-RS-5 Total Score is based on 18 items designed to reflect the symptomatology of ADHD based on the DSM-5 criteria. Each item is scored on a 0 (reflecting no symptoms) to 3 (reflecting severe symptoms) and then added for a total score ranging from 0-54.
- ASHS Physiological factor is the mean of Questions 6, 13, 15, 21, and 22.
- ASHS Behavioral Arousal Factor is the mean of Questions 14, 16, and 31.
- ASHS Cognitive/Emotional Factor is the mean of Questions 12, 17, 18, 19, 20, and 32.
- ASHS Sleep Environment Factor is the mean of Questions 23, 24, 25, 26, and 27.
- ASHS Sleep Stability Factor is the mean of Questions 33, 37, and 39.
- ASHS Daytime Sleep Factor is the mean of Questions 4, and 7.
- ASHS Substances Factor is the mean of Questions 9, and 10.
- ASHS Bedtime Routine Factor is the value for Question 30.
- ASHS Total Score is the mean of all 8 subscales, with a higher score indicating better success on each of the dimensions of sleep hygiene.

SAP FINAL Version 2.0

• SCARED Panic Disorder is the summation of Questions 1, 6, 9, 12, 15, 18, 19, 22, 24, 27, 30, 34, and 38.

- SCARED Generalized Anxiety is the summation of Questions 5, 7, 14, 21, 23, 28, 33, 35, and 37.
- SCARED Separation Anxiety is the summation of Questions 4, 8, 13, 16, 20, 25, 29, and 31
- SCARED Social Anxiety is the summation of Questions 3, 10, 26, 32, 39, 40 and 41.
- SCARED Significant School Avoidance is the summation of questions 2, 11, 17, and 36.
- SCARED Total Score is the summation of all 41 questions, each scored from 0 to 2 scale.
- C-SSRS Suicidal Ideation is an indicator of any subject who experience any one of the five suicidal ideation events at least once (Questions 4, 6, 8, 10, and 12)
- C-SSRS Suicidal Behavior is an indicator of any subject who experience any one of the suicidal behavior events at least once (Questions 22, 26, 29, 32, and 35)
- C-SSRS composite endpoint of Suicidal Ideation or Behavior is an indicator of any subject who experiences any one of the ten suicidal ideation or behavior events at least once.
- TEAE An AE is defined as treatment emergent if the first onset or worsening is after the first administration of IP (NFC-1 or placebo) and not more than 7 days after the last administration of IP
- For the tabulation of TEAE's that are related to study drug, these are defined as any TEAE which is determined by the investigator as 'possibly related' or 'related'.
- Post-Treatment AE is an AE that has started more than 7 days after last administration of IP.
- Prior medications are defined as medications or therapies initiated prior to date of first dose of IP and terminating prior to date of first dose of IP. Medications that are started prior to the date of first dose of IP and are continuing after the first dose of IP are considered to be both prior and concomitant medications
- Concomitant medication is defined as any medication a subject received concurrently with study treatment.
- Post-treatment medication is defined as any medication that has started more than 7 days after the last administration of IP.
- Compliance (Overall) = $(\sum (Individual Week Compliance) * (Time-Weight)) * 100. A subject is non-compliant if they take <math>< 80\%$ or > 120% of IP.
 - Individual Week Compliance is defined as the number of capsules taken at a particular week divided by the expected number of capsules taken at a particular week. Given that a subject will be dose optimized, the number of expected capsules will vary according to which dose the subject is currently on for each day.
 - Time-Weight is the fraction of \mathbf{x}/\mathbf{y} where \mathbf{x} is the number of days in the week the subject is expected to be on dose and \mathbf{y} is the whole treatment duration defined as first dose last dose + 1.

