## 10.1.4 7-day Follow-up Call

At Day 49 (+ 5 days), caregivers will receive a telephone call to assess and record concomitant medication and newly occurring AEs since the last evaluation.

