## 10.2 Study Duration

The overall study duration is expected to be 70 days (including up to 21 days of screening inclusive of a maximum 14 days of wash-out, approximately 42 days of treatment, and a follow-up period of approximately 7 days).

The planned sequence and maximum duration of the study periods will be as follows:

- 1. Screening period: approximately 21 days.
- 2. Wash-out period: if applicable, up to 14 days.
- 3. Dose optimization phase: 28 days.
- 4. Dose maintenance phase: 14 days.
- 5. Follow-up: 7 days (+5 days) after the last dose of IP.

The maximum study duration for each subject is approximately 70 days.

The maximum treatment duration for each subject is 42 days.

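### Under SAP 6.3 a drug started 1 to 7 days after the last dose enters no medication table, and one TEAE footnote omits the 7-day limit

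*SAP*

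**What the plan says.** SAP 6.3 sorts medications into three classes by timing.

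- Prior: "Prior medications are defined as medications or therapies initiated prior to date of first dose of IP". A drug that began before the first dose and continued past it counts as both prior and concomitant.
- Concomitant: "Concomitant medication is defined as any medication a subject received concurrently with study treatment". The footnote to Table 14.3.7 repeats this definition.
- Post-treatment: "Post-treatment medication is defined as any medication that has started more than 7 days after the last administration of IP".

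These classes feed Tables 14.1.5, 14.3.7 and 14.3.8. Listing 16.2.3.2 names all three in its title, but its key has codes only for prior, concomitant and both.

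For adverse events, SAP 6.3 and Protocol 11.1.5 close the treatment-emergent window at the same point: "not more than 7 days after the last administration of IP". SAP 6.3 assigns later onsets to the post-treatment class: "Post-Treatment AE is an AE that has started more than 7 days after last administration of IP". The footnote to the Table 14.3.1.2 shell reads differently: "TEAE is defined as AEs occurring or worsening with an onset at the time of or following the start of treatment with study medication".

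The last planned contact is one telephone call. Protocol 10.2 gives "Follow-up: 7 days (+5 days) after the last dose of IP". Protocol 10.1.4 gives "At Day 49 (+ 5 days), caregivers will receive a telephone call to assess and record concomitant medication and newly occurring AEs since the last evaluation".

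**The concern.** The three medication classes should cover every recorded drug, and they do not. The AE rules carry the on-treatment period forward by 7 days. The post-treatment medication rule starts only after those 7 days, but the concomitant rule was not extended to meet it. A drug started in that week is collected at the call and then summarised nowhere. An AE starting in the same week is tabulated as treatment-emergent, while a drug given for it, or one that might explain it, is missing from every medication summary.

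All ADHD medication is stopped for the study (Protocol 9.12.2) and subjects return to standard care afterwards (Protocol 9.13). This week is therefore a plausible time for drugs to be started, although the documents do not say when that happens.

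The footnote is a separate problem. Without an end date, it makes an AE that starts more than 7 days after the last dose treatment-emergent in one table, while SAP 6.3 sends the same event to the post-treatment table.

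**Working it through.** **1. The plan's own timeline.** Treatment is 28 + 14 = 42 days (Protocol 10.2). The call falls on 42 + 7 = Day 49. The total is 21 + 42 + 7 = 70 days. All three agree with the protocol.

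**2. Classification by start or onset day.** Apply the SAP 6.3 definitions to a drug started, or an AE first occurring, after treatment has begun:

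| Start relative to last dose | Prior | Concomitant | Post-treatment medication | AE class (SAP 6.3) |
|---|---|---|---|---|
| On or before the last-dose date | No | Yes | No | TEAE |
| Days 1 to 7 after | No | No | No | TEAE |
| Day 8 or later | No | No | Yes | Post-treatment AE |

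The middle row is the gap. It exists for medications only; every AE has a class.

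**3. Time that can feed Table 14.3.8.** Let c be the day of the call, counted from the last dose. Qualifying days = max(0, c − 7). The share of post-dose time in the gap = 7/c.

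- c = 7 (planned day): 0 qualifying days; gap share 7/7 = 100%.
- c = 9: 2 qualifying days; gap share 7/9 = 78%.
- c = 12 (latest under Protocol 10.2): 5 qualifying days; gap share 7/12 = 58%.

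Protocol 10.1.4 instead fixes the call at Day 49 to 54, and Visit 8 has a window of ±2 days around Day 42. If the last dose is on Day 40 and the call on Day 54, c = 14 and the qualifying time is 7 days. With the same last dose and a call on Day 49, c = 9 and it is 2 days. The overall range is 0 to 7 days.

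With the 80 expected completers, the gap covers 80 × 7 = 560 person-days if every call is at least 7 days after the last dose. Under the Protocol 10.2 timing, the time that can feed Table 14.3.8 is 0 to 80 × 5 = 400 person-days.

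**4. The TEAE footnote.** Take an AE that starts 9 days after the last dose. Under SAP 6.3 and Protocol 11.1.5 it is not a TEAE, and under SAP 6.3 it is a post-treatment AE. Under the Table 14.3.1.2 footnote it is a TEAE, because onset follows the start of treatment and no end is given. Followed literally, the event is counted in both Table 14.3.1.2 and Table 14.3.1.4. The programming note for Table 14.3.1.4 also asks for the TEAE definition to be added to that table's footnote, although the table is for post-treatment events.

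**5. After the change.** If a post-treatment medication is any drug started after the last-dose date, the window is 7 days for a day-7 call and 12 days for a day-12 call. The middle row then has a class.

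**The case against.** The strongest reply is that little is at stake. SAP 6.2 puts all collected data in listings. Listing 16.2.3.2 shows start date, end date and indication, so a gap drug can still be seen. Frequency tables by ATC class never link a drug to an AE in any case. The protocol uses the term concomitant for what is recorded at the follow-up call, so a programmer might well place gap drugs in Table 14.3.7. Appendix A says the shells are programming guidance that can be updated separately from the SAP.

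Most of this stands, and it makes the point minor. It does not close the gap. The SAP's concomitant definition, repeated under Table 14.3.7, does not admit these drugs, so the count would depend on the programmer. That shells are easy to update is a reason to correct the footnote and the listing key, not to leave them.

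A reader might infer more than the documents support:

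- **That AEs are lost or misclassified.** They are not. The 7-day TEAE window is the protocol's own, and SAP 6.3 assigns every later onset to the post-treatment class.
- **That Table 14.3.1.4 fails in a purpose of showing discontinuation effects.** No section gives it that purpose. Protocol 13.4.4.1 plans summaries of post-treatment AEs, and a sparse residual table is what a 7-day window with a 7 (+5)-day follow-up produces. Splitting TEAEs at the last dose is a preference, not a correction.
- **That the post-treatment tables must be almost empty.** That is exact only for a call 7 days after the last dose. As an illustration, assume 0.25 to 1.0 AE per subject per 28 days and 80 completers. If every call came on day 12, the expected number of post-treatment AEs would be 80 × 0.25/28 × 5 = 3.6 to 80 × 1.0/28 × 5 = 14.3. The AE rate is an assumption; the documents give none for this period.

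**Conclusion.** Two defects hold on the stated rules. First, a drug started 1 to 7 days after the last dose belongs to no medication class and no medication table. Those days make up 58% to 100% of post-dose time for calls 7 to 12 days after the last dose. Second, the Table 14.3.1.2 footnote contradicts the TEAE limit in SAP 6.3 and Protocol 11.1.5, and would double count any AE starting beyond day 7.

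Both are minor corrections to safety reporting. No efficacy result depends on these tables, and gap drugs remain in the listing. How many drugs would be affected cannot be derived from the documents.

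The arithmetic assumes completers who are called as planned. For early terminators, Protocol 11.2 ends AE collection at the earlier of the follow-up contact and the early termination visit, whereas Protocol 9.9 gives subjects who stop for intolerability a 7-day call. These two sections need to be reconciled before any post-treatment window can be stated for that group.

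**What to change.** - In SAP 6.3, define a post-treatment medication as any medication started after the date of the last dose. Drugs started on or before that date keep their present class.
- Add a post-treatment code to the key of Listing 16.2.3.2.
- Replace the TEAE footnote of Table 14.3.1.2 with the SAP 6.3 definition, and carry the SAP 6.3 post-treatment AE definition into the footnote of Table 14.3.1.4.
- Leave the TEAE and post-treatment AE definitions as they are. Moving days 1 to 7 into the post-treatment AE table would count those events twice.
- Footnote Table 14.3.1.4 to say that follow-up is planned to end 7 (+5) days after the last dose, so few or no events can qualify and a low count is not evidence that none occurred.

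The cost is a few lines of SAP and shell text. No new data are needed. The length of the post-treatment window will still vary with the day of the call, which the footnote makes plain.
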